9.8.1 Liver Function Tests

The central laboratory will notify the medical monitor of alanine transaminase (ALT) or aspartate transaminase (AST) $>3 \times$ upper limit of normal (ULN) and total bilirubin $>2 \times$ ULN that are derived from centrally submitted samples.

Subjects with new treatment-emergent ALT or AST elevations of $>3 \times$ ULN, with or without total bilirubin $>2 \times$ ULN, must be followed closely, including confirmatory testing performed by the central laboratory within 48 to 72 hours of the initial finding and subsequent close monitoring of ALT, AST, and bilirubin levels, as clinically indicated.

If a subject cannot return to the site for confirmatory testing, a local laboratory may be used. Local laboratory results must be reported immediately to the medical monitor, and the subject must have the tests repeated and sent to the central laboratory as soon as possible (ideally within 48 to 72 hours).

Study drug administration **must be interrupted** immediately (prior to confirmatory testing) if any of the following criteria are met:

- ALT or AST $>8 \times$ ULN
- ALT or AST $>5 \times$ ULN for more than 2 weeks
- ALT or AST $>3 \times$ ULN, in association with total bilirubin $>2 \times$ ULN and/or clinical jaundice

A thorough investigation of potential causes should be conducted, and the subject should be followed closely for clinical progression.

Subjects who enroll in this study on a drug interruption because of transaminase elevations in a parent study may NOT receive the first dose of study drug until transaminases return to baseline values or $\leq 2 \times$ ULN, whichever is higher.

Study drug administration **must be discontinued** if the following criteria are met:

- Subsequent ALT or AST values confirm the initial elevation that satisfied the interruption rule (above), and no convincing alternative etiology (e.g., acetaminophen use, viral hepatitis, alcohol ingestion) is identified, regardless of whether transaminase levels have improved

All subjects in whom treatment is discontinued for elevated transaminases (and bilirubin, as applicable) should have these levels monitored closely until levels normalize or return to baseline.

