If an alternative, reversible cause of transaminase elevation with or without increased bilirubin or clinical jaundice has been identified, study drug administration may be resumed once transaminase levels return to baseline or are $\leq 2 \times$ ULN, whichever is higher. Regardless of the duration of interruption, the medical monitor should be notified before resumption of study drug. Upon resumption of study drug, transaminases and bilirubin should be assessed weekly for 4 weeks. If a protocol-defined transaminase elevation interruption threshold recurs within 4 weeks of rechallenge with the study drug (with confirmation of the initial elevation by repeat testing within 48 to 72 hours), then the study drug must be permanently discontinued, regardless of the presumed etiology.

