12.3.4.1 Adverse Events

For analysis purposes, AEs will be classified as pretreatment AEs, TEAEs, or post-treatment AEs, defined as follows:

- **Pretreatment AE:** any AE that occurred since the end of the TE Period in the parent study and before the first dose of ELX/TEZ/IVA in the TE Period in the open-label study
- **TEAE:** any AE that worsened (either in severity or seriousness) or newly developed at or after the first dose date of ELX/TEZ/IVA in the TE Period in this open-label study
- **Post-treatment AE:** any AE that worsened (either in severity or seriousness) or newly developed after the TE Period in this open-label study

For AEs with missing or partial start dates, if there is no clear evidence that the AEs started before or after study drug treatment, then the AEs will be classified as TEAEs.

AE summary tables will be presented for TEAEs only and will include the following:

- All TEAEs
- TEAEs by strongest relationship
- TEAEs by maximum severity
- TEAEs leading to treatment discontinuation
- TEAEs leading to treatment interruption
- Serious TEAEs
- TEAEs leading to death
- Grade 3 and Grade 4 TEAEs
- Frequently reported TEAEs

Summaries will be presented by MedDRA SOC and PT using frequency counts and percentages (i.e., number and percentage of subjects with an event). When summarizing the number and percentage of subjects with an event, subjects with multiple occurrences of the same AE or a continuing AE will be counted once, only the maximum severity level will be presented in the severity summaries, and the strongest relationship level in the relationship summaries.

Listings containing individual subject level AE data will be provided separately for:

- Serious TEAEs
- TEAEs leading to treatment discontinuation
- TEAEs leading to treatment interruption
- TEAEs leading to death

In addition, all AEs, including pre- and post-treatment AEs, will be presented in individual subject data listings

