8.4.1 Adverse Events

For analysis purposes, AEs will be classified as pretreatment AEs, TEAEs, and post-treatment AEs, defined as follows:

- **Pretreatment AE:** any AE before the first dose of ELX/TEZ/IVA in the TE Period in this OLE study
- **TEAE:** any AE that worsened (either in severity or seriousness) or newly developed at or after the first dose date of ELX/TEZ/IVA in the TE Period in this OLE study
- **Post-treatment AE:** any AE that worsened (either in severity or seriousness) or newly developed after the TE Period in this OLE study

For AEs with missing or partial start dates, if there is no clear evidence that the AEs started before or after study drug treatment, then the AEs will be classified as TEAEs. Details for imputing missing or partial start dates of adverse events are described in [Appendix D](#).

An overview of all TEAEs for the OL-SS during the TE Period will be summarized overall and include the following categories:

- Number of TEAEs (total number of TEAEs only)
- Subjects with any TEAEs
- Subjects with TEAEs by strongest relationship
- Subjects with TEAEs by maximum severity
- Subjects with TEAEs leading to treatment discontinuation
- Subjects with TEAEs leading to treatment interruption
- Subjects with Grade 3/4/5 TEAEs
- Subjects with related TEAEs
- Subjects with serious TEAEs
- Subjects with related serious TEAEs
- Subjects with TEAE leading to death

The frequency counts and percentages, as well as the exposure adjusted event rate, will be presented for the above overview table. The exposure adjusted rate will not be presented for strongest relationship and maximum severity categories.

The following summary tables of TEAEs will be presented overall:

- All TEAEs
- Grade 3/4/5 TEAEs
- TEAEs by strongest relationship
- TEAEs by maximum severity
- TEAEs leading to treatment discontinuation
- TEAEs leading to treatment interruption
- Related TEAEs
- Serious TEAEs
- Related serious TEAEs
- TEAEs leading to death

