Summaries will be presented by MedDRA System Organ Class (SOC) and Preferred Term (PT) using frequency counts, percentages (i.e., number and percentage of subjects with an event), and the exposure adjusted event rate (except for summary by strongest relationship and maximum severity). When summarizing the number and percentages of subjects, subjects with multiple occurrences of the same adverse event or a continuing adverse event will be counted once, and only the maximum severity level will be presented in the severity summaries, and the strongest relationship level in the relationship summaries. Missing severity levels will not be included in the Grade 3/4/5 TEAE summaries; missing relationship will be considered as related and included in the related TEAE and related serious TEAE summaries.

An additional summary table in which the frequency counts and percentages as well as the exposure adjusted event rate will be presented for TEAEs during the OL safety period:

- All TEAEs by PT

All AEs, including pretreatment AEs, TEAEs, and post-treatment AEs, will be presented in an individual subject data listing based on the OL-AS. In addition, separate listings containing individual subject adverse event data for TEAEs leading to treatment discontinuation, TEAEs leading to treatment interruption, Grade 3/4/5 TEAEs, SAEs and all deaths will be provided, with a flag indicating the TEAE status for SAEs and deaths.

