Appendix D: Imputation Rules for Missing AE dates

Imputation rules for missing or partial AE start date are defined below. If the imputed AE start date is before the study informed consent/assent date, the AE start date will be imputed using the study informed consent/assent date.

- **If only Day of AE start date is missing:**

- If the full (or partial) AE end date is NOT before the first dose date of the Treatment Period or AE end date is missing, then
 - if AE start year and month are equal to the month and year of first dose date of the Treatment Period, then impute the AE start day as the day of first dose date of the Treatment Period;
 - else impute the AE start day as 1.
- else impute the AE start day as 1.

Compare the imputed AE start date with TE period to determine whether the AE is pretreatment AE, TEAE or post-treatment AE.

- **If Day and Month of AE start date are missing:**

- If the full (or partial) AE end date is NOT before the first dose date of the Treatment Period or AE end date is missing, then
 - if AE start year is equal to the year of first dose date of the Treatment Period, then impute the AE start month and day as the month and day of first dose date of the Treatment Period;
 - else impute the AE start month as January and day as 1.
- else impute the AE start month as January and day as 1.

Compare the imputed AE start date with TE period to determine whether the AE is pretreatment AE, TEAE or post-treatment AE.

- **If Year of AE start date is missing:**

If the year of AE start is missing or AE start date is completely missing then query site and

- If the full (or partial) AE end date is NOT before the first dose date of the Treatment Period or AE end date is missing, then impute the AE start date as the first dose date of the Treatment Period;
- else impute the AE start date as the informed consent/assent date.

Imputation rules for partial AE end date are defined below:

- Impute the AE end date as min (the last day of the month, end of study participation) if day is missing, or min (Dec, end of study participation) if month is missing.

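### An AE that began before the first extension dose and interrupts or ends study drug, with no rise in severity or seriousness, is missing from the AE discontinuation and interruption tables

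*Protocol*

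**What the plan says.** Protocol section 12.3.4.1 and SAP section 8.4.1 use the same rule: a TEAE is "any AE that worsened (either in severity or seriousness) or newly developed at or after the first dose date of ELX/TEZ/IVA" in this study. The action taken with study drug plays no part in it. The treatment-emergent (TE) Period opens at the first dose in the extension (protocol 12.3.1, SAP 8.1), not at the first ELX/TEZ/IVA dose a subject ever took.

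The outputs follow that rule. The protocol states: "AE summary tables will be presented for TEAEs only and will include the following". The SAP overview table has rows such as "Subjects with TEAEs leading to treatment interruption", and the SAP also promises "separate listings containing individual subject adverse event data for TEAEs leading to treatment discontinuation, TEAEs leading to treatment interruption". In SAP 8.4.1.1, the lines for elevated transaminases and rash cover treatment-emergent events only.

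The two documents differ on AEs with earlier onset. For the protocol, a pretreatment AE is one arising between the end of the parent study's TE Period and the first extension dose. For the SAP, it is any AE before the first extension dose.

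**The concern.** This is a rollover study, so some AEs may be ongoing when the first extension dose is given. Inclusion criterion 4 (protocol 8.1) expressly admits subjects who had drug interruptions in the parent study. If an ongoing AE stays at the same grade and drug is later interrupted or withdrawn because of it, the decision falls inside the TE Period but the AE fails the TEAE test.

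Tolerability is part of the primary objective and the primary endpoint, and the tables of AEs that interrupt or end treatment bear on it directly. Leaving such AEs out can only lower the counts in those tables. The AEs left out are the persistent ones, which a long-term extension is well placed to observe.

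**Working it through.** No figure in the plan bears on this point, so there is none to reproduce. The check applies the TEAE rule to one case and traces that case through each planned output.

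**The case.** A recorded AE is known to have begun before the first extension dose. It is unchanged in severity and seriousness, and study drug is interrupted or withdrawn because of it during the TE Period.

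**Step 1: classification.** Onset precedes the first extension dose, so the AE is not newly developed. Neither severity nor seriousness rises, so it has not worsened in the sense of the rule. It is not a TEAE in either document. With onset inside the parent study's TE Period, it fits none of the protocol's three AE classes; under the SAP it is pretreatment.

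**Step 2: outputs.**

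| Output | Place | Is the case shown? |
|---|---|---|
| Tables of AEs leading to discontinuation or interruption | Protocol 12.3.4.1, SAP 8.4.1 | No, TEAEs only |
| Separate listings for the same two categories | Protocol 12.3.4.1, SAP 8.4.1 | No, TEAEs only; the SAP's TEAE-status flag covers only SAEs and deaths |
| Transaminase and rash lines | SAP 8.4.1.1 | No, treatment-emergent events only |
| Disposition | Protocol 12.3.2.1, SAP 8.2.1 | Discontinuations by reason; interruptions not at all |
| Compliance | Protocol 12.3.2.4, SAP 8.2.6 | Interruption days, without cause |
| Listing of all AEs | Protocol 12.3.4.1, SAP 8.4.1 | Yes if the AE is in this study's database, but without counts |

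**Step 3: can the case arise under the plan's own rules?** Protocol 9.8.1 requires interruption when ALT or AST stays above 5 x ULN for more than two weeks. That rule depends on duration, so an unchanged elevation can trigger it. If the elevation is first found 7 days before Day 1, 14 days have elapsed on Day 8 (14 - 7 = 7 days after Day 1), and the limit is exceeded from Day 9. A same-grade symptom that persists until the family stops treatment gives the same result.

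**Step 4: scale.** Expected enrolment is about 108 (protocol 12.1). Each affected subject is 1/108 = 0.93 percentage points. The number affected, k, is an assumption, shown with exact (Clopper-Pearson) 95% intervals:

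| k | k/108 | 95% CI |
|---|---|---|
| 0 | 0.0% | 0 to 3.4% |
| 1 | 0.9% | 0.02 to 5.1% |
| 2 | 1.9% | 0.2 to 6.5% |
| 3 | 2.8% | 0.6 to 7.9% |

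**The case against.** The strongest reply is that the gap is narrow and most of its content can be seen elsewhere. Much of this stands.

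- Both documents list all AEs, and protocol 13.1.1.3 records the action taken for each. Discontinuations are counted by reason whatever the TEAE status. A transaminase case would also show in the laboratory threshold, shift and scatter outputs (SAP 8.4.2, Appendix E), which use TE Period values regardless of AE onset. A laboratory table does not show that drug was interrupted, however, and no table gives interruptions by causing event once the AE is not a TEAE.
- AEs with missing or partial start dates default to TEAE unless there is clear evidence of timing. The gap therefore concerns AEs known to have begun earlier.
- An investigator may record the change as a new or worsened AE. Protocol 13.1.1.1 counts a rise in frequency as worsening, and 13.1.1.2 treats a test result as clinically significant if it leads to a dose change or discontinuation. Neither turns an unchanged ongoing AE into a TEAE.
- How ongoing parent-study AEs enter this database may be settled in CRF completion guidelines that are not among these documents.

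A reader might infer that the clearest victims are "Subjects who enroll in this study on a drug interruption because of transaminase elevations in a parent study" who must later stop under the rule that begins "If a protocol-defined transaminase elevation interruption threshold recurs within 4 weeks of rechallenge with the study drug". The documents do not support that. Section 9.8.1 withholds the first extension dose until transaminases have come back to baseline or to no more than 2 x ULN, whichever is higher. A later threshold crossing would then normally be a new or worsened event after that dose, hence a TEAE.

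A reader might also think that adding drug action to the TEAE definition is the simplest cure. It would do more than that. It would change all TEAE counts and exposure-adjusted rates, and it would give the time-to-onset summary in SAP 8.4.1.1 onset dates earlier than its own reference, the first extension dose. The safety baseline definition also allows the first ELX/TEZ/IVA dose to fall in this study. For such subjects, a parent-study AE began without the drug and would be counted as treatment-emergent.

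**Conclusion.** The point holds as a reporting gap of limited size. On the text of both documents, a recorded AE with known earlier onset and no rise in severity or seriousness is absent from the discontinuation and interruption tables, their separate listings and the special-interest lines, even when the drug action falls in the TE Period. The omission can only lower those counts. For discontinuations, the disposition and AE tables may disagree. For interruptions, nothing is tabulated by causing event.

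The documents do not support a claim that the tables are materially wrong. They give no rates, so the number affected cannot be derived and may be zero. A reader might compute large relative errors: one omitted among 2 to 5 discontinuations is 1/5 to 1/2, or 20% to 50%; one of 10 to two of 5 interruptions is 10% to 40%. Those ranges assume both the event counts and at least one omission. The only firm scale is 0.93 percentage points per subject, given about 108 enrolled. Nor are the events lost altogether, provided they are entered in this study's database. The change is a cheap improvement.

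**What to change.** Leave the TEAE definition and the TEAE tables as they are. In SAP 8.4.1 and 8.4.1.1, and in protocol 12.3.4.1, add to the discontinuation and interruption summaries and listings a separate row or count. It should cover every AE for which drug was interrupted or withdrawn during the extension TE Period, whatever the onset date. Flag each for TEAE status, as SAP 8.4.1 already does for SAEs and deaths, and for onset before or after the first ELX/TEZ/IVA dose.

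Two supporting edits are needed. Align the protocol's definition of a pretreatment AE with the SAP's, so that AEs with onset in the parent study's TE Period have a class. Make sure the extension CRF captures the action taken for ongoing parent-study AEs; protocol 13.1.1.3 is a natural place to say so.

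The cost is one extra row, the flags and a line of CRF guidance. Action taken is already a recorded field for each AE (protocol 13.1.1.3 and 13.1.1.6). Some events may also appear in the parent-study report, which the flags make visible. No dosing or stopping rule changes.

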12.3.4.2 Clinical Laboratory Assessments

For the TE laboratory measurements, the observed values and change from baseline values of the continuous laboratory parameters will be summarized in SI units at each time point during the TE Period.

For threshold analysis, the number and percentage of subjects with at least 1 threshold event during the TE Period will be summarized. The threshold criteria and selected parameters will be provided in the SAP.

Results of urinalysis and pregnancy tests will be listed in individual subject data listings only. In addition, a listing containing individual subject laboratory assessment values will be provided. This listing will include data from scheduled and unscheduled time points.

Additional safety laboratory data analyses may be described in the SAP.

12.3.4.3 Electrocardiogram

For the TE ECG measurements, a summary of observed values and change from baseline values will be provided at each time point during the TE Period, for the following ECG interval measurements (in msec): RR, PR, QT, QT corrected for heart rate (HR) intervals (QTcF), QRS duration, and HR (beats per minute).

For threshold analysis, the number and percentage of subjects with at least 1 threshold event during the TE Period will be summarized. The threshold criteria will be provided in the SAP.

Additional ECG analyses may be described in the SAP.

12.3.4.4 Vital Signs

For the TE vital signs measurements, the observed values and change from baseline values will be summarized at each time point during the TE Period in this open-label study. The following vital signs parameters will be summarized: systolic and diastolic blood pressure (mm Hg), body temperature (°C), pulse rate (beats per minute), and respiratory rate (breaths per minute).

For threshold analysis, the number and percentage of subjects with at least 1 threshold event during the TE Period will be summarized. The threshold criteria will be provided in the SAP.

Additional vital signs analyses may be described in the SAP.

12.3.4.5 Pulse Oximetry

For the TE pulse oximetry measurements, a summary of observed values and change from baseline values will be provided at each time point during the TE Period, for the percent of oxygen saturation by pulse oximetry.

12.3.4.6 Physical Examination

No tables/figures/listings will be provided for PE data.

12.3.4.7 Other Safety Analyses

Details of other safety analyses may be included in the SAP.

12.4 Interim Analysis

Interim analyses may take place at any time at the discretion of the sponsor.

12.5 Data Monitoring Committee Analysis

A data monitoring committee (DMC) will conduct periodic safety review(s) of study data as outlined in the DMC charter.

13 PROCEDURAL, ETHICAL, REGULATORY, AND ADMINISTRATIVE CONSIDERATIONS

13.1 Adverse Event and Serious Adverse Event Documentation, Severity Grading, and Reporting

13.1.1 Adverse Events

13.1.1.1 Definition of an Adverse Event

An AE is defined as any untoward medical occurrence in a subject during the study; the event does not necessarily have a causal relationship with the treatment. This includes any newly occurring event or worsening of a pre-existing condition (e.g., increase in its severity or frequency) after the ICF is signed.

An AE is considered serious if it meets the definition in Section 13.1.2.1.

13.1.1.2 Clinically Significant Assessments

Study assessments including laboratory tests, ECGs, PEs, and vital signs will be assessed and those deemed to have clinically significant worsening from baseline will be documented as an AE. When possible, a clinical diagnosis for the study assessment will be provided, rather than the abnormal test result alone (e.g., urinary tract infection, anemia). In the absence of a diagnosis, the abnormal study assessment itself will be listed as the AE (e.g., bacteria in urine or decreased hemoglobin).

An abnormal study assessment is considered clinically significant if the subject has 1 or more of the following:

- Concomitant signs or symptoms related to the abnormal study assessment
- Further diagnostic testing or medical/surgical intervention
- A change in the dose of study drug or discontinuation from the study

Repeat testing to determine whether the result is abnormal, in the absence of any of the above criteria, does not necessarily meet clinically significant criteria. The determination of whether the study assessment results are clinically significant will be made by the investigator.

A laboratory value that is Grade 4 will not automatically be an SAE. A Grade 4 laboratory value will be an SAE if the subject's clinical status indicates a life-threatening AE.

